2.2.1 Subgroup of interest

Three age subgroups (6-10 years, 11-17 years, and ≥ 18 years) will be separately presented in additional to overall summaries. This will apply to all post-text tables and listings that will be defined in the mock shells document.

2.3 Patient disposition, demographics and other baseline characteristics

Descriptive statistics for demographics (age, sex, race and ethnicity), baseline characteristics (height, body weight, systolic and diastolic blood pressure, radial pulse rate, respiratory rate, and body temperature), and summaries of relevant disease history/current medical condition including CF signs and symptoms will be presented for SAF set overall and by age subgroup.

Number of patients included in each analysis set (SF and SAF) will be reported, as well as reasons for screen failures. Patient dispositions (number of patients who completed/discontinued the study with discontinuation reasons) and protocol deviations will be reported for safety set.

2.4 Treatments (study treatment, rescue medication, concomitant therapies, compliance)

2.4.1 Study treatment / compliance

Treatment (placebo) compliance is part of HF assessments and will be summarized in the HF report.

2.4.2 Prior, concomitant and post therapies

Prior and concomitant medications will be coded using the WHO Drug Reference List, which employs the Anatomical Therapeutic Chemical (ATC) classification system. Concomitant procedures, non-drug therapies and adverse events will be coded using the Medical Dictionary for Drug Regulatory Activities (MedDRA) terminology.

Standard summary tables of concomitant medications by ATC class and non-drug therapies will be provided.

2.5 Safety analyses

2.5.1 Adverse events (AEs)

Adverse events and SAEs will be coded according to the MedDRA coding system using the latest version at the time of generating the report.

AEs and SAEs will be summarized by system organ class (SOC) and preferred term (PT) for the safety set overall and by age subgroups. The same event, as defined by preferred term, will be counted only once for each subject.

The maximum AE severity and AEs resulting in withdrawal of treatment will also be summarized by SOC and preferred term.

Note: Summary tables will only be provided if at least five patients report any AE.

In addition to the tabulations, listings will be provided for AEs and SAEs.

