6.1 Information to be collected on screening failures

Subjects who are screened but are recognized to have not met all inclusion and exclusion criteria will be considered as screening failures. The study completion page for the screening period will be completed and data on demographics, inclusion/exclusion, and serious adverse event (SAE) will be collected for these patients. Adverse events that are not SAEs will be followed by the investigator and collected only in the source data.

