7.1 Adverse events

An AE is any untoward medical occurrence (e.g., any unfavorable and unintended sign [including abnormal laboratory findings], symptom or disease) in a subject or clinical investigation subject *after providing written informed consent* for participation in the study until the end of study visit. Therefore, an AE may or may not be temporally or causally associated with the use of a medicinal (investigational) product.

The occurrence of adverse events must be sought by non-directive questioning of the patient at each visit during the study. Adverse events also may be detected when they are volunteered by the patient during or between visits or through physical examination findings, laboratory test findings, or other assessments.

Abnormal laboratory values or test results constitute adverse events only if they fulfill at least one of the following criteria:

- they induce clinical signs or symptoms,
- they are considered clinically significant,
- they require therapy.

Clinically significant abnormal laboratory values or test results must be identified through a review of values outside of normal ranges/clinically notable ranges, significant changes from baseline or the previous visit, or values which are considered to be non-typical in patient with underlying disease. Investigators have the responsibility for managing the safety of individual patient and identifying adverse events.

Adverse events must be recorded in the appropriate CRF capturing AEs under the signs, symptoms or diagnosis associated with them, accompanied by the following information:

- the severity grade
 - mild: usually transient in nature and generally not interfering with normal activities
 - moderate: sufficiently discomforting to interfere with normal activities
 - severe: prevents normal activities
- its relationship to the study treatment
- its duration (start and end dates) or if the event is ongoing an outcome of not recovered/not resolved must be reported.
- whether it constitutes a serious adverse event (SAE - See [Section 7.2](#) for definition of SAE) and which seriousness criteria have been met.
- action taken regarding study treatment

All adverse events must be treated appropriately. Treatment may include one or more of the following:

- [investigational] treatment dose not changed (e.g. further observation only)
- [investigational] treatment dose increased/reduced
- [investigational] treatment interrupted/withdrawn

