7.2 Serious adverse events

7.2.1 Definition of SAE

An SAE is defined as any adverse event [appearance of (or worsening of any pre-existing)] undesirable sign(s), symptom(s) or medical condition(s) which meets any one of the following criteria:

- is fatal or life-threatening
- results in persistent or significant disability/incapacity
- constitutes a congenital anomaly/birth defect
- requires inpatient hospitalization or prolongation of existing hospitalization, unless hospitalization is for:
 - routine treatment or monitoring of the studied indication, not associated with any deterioration in condition
 - elective or pre-planned treatment for a pre-existing condition that is unrelated to the indication under study and has not worsened since signing the informed consent
 - treatment on an emergency outpatient basis for an event not fulfilling any of the definitions of a SAE given above and not resulting in hospital admission
 - social reasons and respite care in the absence of any deterioration in the patient's general condition
- is medically significant, e.g. defined as an event that jeopardizes the patient or may require medical or surgical intervention.

All malignant neoplasms will be assessed as serious under “medically significant” if other seriousness criteria are not met.

Life-threatening in the context of a SAE refers to a reaction in which the patient was at risk of death at the time of the reaction; it does not refer to a reaction that hypothetically might have caused death if it were more severe (please refer to Annex IV, ICH-E2D Guideline).

Medical and scientific judgment should be exercised in deciding whether other situations should be considered serious reactions, such as important medical events that might not be immediately life threatening or result in death or hospitalization but might jeopardize the patient or might require intervention to prevent one of the other outcomes listed above. Examples of such events are intensive treatment in an emergency room or at home for allergic bronchospasm, blood dyscrasias or convulsions that do not result in hospitalization or development of dependency or abuse (please refer to Annex IV, ICH-E2D Guideline).

Any suspected transmission via a medicinal product of an infectious agent is also considered a serious adverse reaction.

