7.2.2 SAE reporting

To ensure patient safety, every SAE, regardless of causality, occurring after the patient has provided informed consent and until 30 days after the last study visit must be reported to the Sponsor’s safety department within 24 hours of learning of its occurrence. Any SAEs experienced after the 30-day period after the last study visit should only be reported to the Sponsor’s safety if the investigator suspects a causal relationship to study treatment.

All follow-up information for the SAE including information on complications, progression of the initial SAE and recurrent episodes must be reported as follow-up to the original episode within 24 hours of the investigator receiving the follow-up information. An SAE occurring at a different time interval or otherwise considered completely unrelated to a previously reported one must be reported separately as a new event.

Information about all SAEs is collected and recorded on the Serious Adverse Event Report Form; all applicable sections of the form must be completed in order to provide a clinically thorough report. The investigator must assess the relationship of each SAE to study treatment, complete the SAE Report Form in English, and submit the completed form within 24 hours to the Sponsor. Detailed instructions regarding the submission process and requirements for signature are to be found in the investigator folder provided to each site.

Follow-up information is submitted as instructed in the investigator folder. Each re-occurrence, complication, or progression of the original event must be reported as a follow-up to that event regardless of when it occurs. The follow-up information should describe whether the event has resolved or continues, if and how it was treated, whether the blind was broken or not, and whether the patient continued or withdrew from study participation.

Information about common risks with inhalation of placebo powder will be included in the informed consent and should be discussed with the patient during the study as needed.

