2.2 Analysis sets

Two analysis sets are defined in the protocol:

The Screen Failure Set (SF) includes all patients who signed the informed consent and failed the screening.

The Safety set (SAF) includes all patients who entered the study and who have inhaled the contents of at least one capsule of placebo, regardless of whether the related HF assessment is completed.

NOTE: SAF set will be used for all analyses discussed in this document.

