2.5.2 Deaths

Deaths if any occurred will be reported by a listing including all relevant information as collected on SAE eCRF pages.

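### SAEs in consented subjects outside the Safety Set are collected but have no SAP output, and the population for the deaths listing is unclear

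*SAP*

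**What the plan says.** **Collection (protocol).** Section 7.2.2 covers every SAE, whatever its cause, "occurring after the patient has provided informed consent and until 30 days after the last study visit must be reported". Section 6.1 adds that for screen failures "data on demographics, inclusion/exclusion, and serious adverse event (SAE) will be collected for these patients"; their non-serious AEs stay in source data only. On the record used, 7.2.2 says "Information about all SAEs is collected and recorded on the Serious Adverse Event Report Form".

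**Reporting (SAP).** Section 2.5.1 says "AEs and SAEs will be summarized by system organ class (SOC) and preferred term (PT) for the safety set overall and by age subgroups". It also promises listings of AEs and SAEs, without naming a population for them. Section 2.2 supplies one through its note: "SAF set will be used for all analyses discussed in this document". The Safety Set is defined there as subjects who entered the study and inhaled the contents of at least one capsule. The Screen Failure Set is also defined in 2.2, but SAP 2.3 uses it only for counts and reasons for failure. Section 2.5.2 says "Deaths if any occurred will be reported by a listing including all relevant information as collected on SAE eCRF pages" and names no analysis set.

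**Protocol analysis rule.** The opening of protocol section 9 bases the safety analysis on subjects who inhaled at least one capsule's contents, and protocol 9.1 defines the Safety Set the same way.

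**The concern.** The population from which SAEs are collected is wider than the population for which they are reported. Any SAE that falls in the difference reaches the sponsor but appears in no table or listing the SAP defines.

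One part of that difference matters for this study in particular. Protocol 3.2.2 and 13.6.1 name choking as one of two hazards of device use, and 3.7.2 says a subject could inhale a whole capsule. A subject who chokes on the first capsule and stops may never have inhaled its contents in the sense of the Safety Set definition. Read literally, a serious event from a hazard the study names could then be missing from the clinical safety output, and an SAE listing could be empty although an SAE had been recorded. The protocol itself rates serious harm from choking as very unlikely. The concern is completeness of the report, not an expected number of events.

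**Working it through.** No sample size, power or event count is involved, so the check sets the two populations side by side.

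| Group of consented subjects | SAEs collected? | In Safety Set? | SAP output for an SAE |
|---|---|---|---|
| Inhaled at least one capsule's contents | Yes (protocol 7.2.2) | Yes | Tables and listing (SAP 2.5.1) |
| Enrolled, but did not inhale a capsule's contents | Yes (protocol 7.2.2) | No (SAP 2.2) | None under the 2.2 note |
| Screen failure | Yes (protocol 6.1 and 7.2.2) | No (SAP 2.2) | None; SAP 2.3 gives only counts and reasons |

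1. **Second row.** This group is in neither SAP analysis set: these subjects did not fail screening and did not meet the inhalation condition. Protocol 5.5.1 foresees patients who do not start inhalation, and 5.6.2 foresees stopping before the dose is complete.

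2. **Listings.** SAP 2.5.1 provides summary tables only if at least five patients report any AE. Below that number the listings are the whole AE and SAE output, so their population decides what is visible. Only the general note in 2.2 sets that population.

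3. **Deaths.** Section 2.5.2 can be read in two ways. Under the 2.2 note it covers the Safety Set. On its own words it covers any death on the SAE pages of the eCRF. The SAP does not settle which.

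4. **Source.** The SAP covers eCRF data only (SAP 1), while the SAE record named in protocol 7.2.2 is the Report Form. Protocol 7.1 has the AE page of the CRF record whether an event is serious, so SAE data in the eCRF do not conflict with the protocol. No section says, however, that an SAE starting after the single visit is entered in the clinical database, and no reconciliation is specified.

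5. **Size.** The number screened is not given, nor is any SAE rate. The planned difference between about 50 enrolled and 45 completing (50 − 45 = 5) does not measure the second row: a non-completer may have inhaled one or more capsules and so be in the Safety Set. The gap therefore cannot be quantified from the documents.

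**The case against.** The restriction is not the SAP's invention. Protocol section 9 and 9.1 set the same safety population, so the SAP follows the protocol. That stands, and it makes this a reporting gap and not a deviation.

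The note in SAP 2.2 is also not absolute, since 2.3 reports screen-failure counts. One could argue that a listing is not an analysis, that 2.5.2 already covers any death, and that the shells deferred in SAP 2 may settle the matter. This stands in part. It is why the deaths population is ambiguous and not clearly restricted. But the choice of population belongs in the SAP, and its only general statement points to the Safety Set.

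The stakes are limited. SAEs still go to the sponsor's safety department within 24 hours of the site learning of them, the clinical data are supplementary to the human factors results, and nothing is tested. That stands too. It argues for a small change, not for none.

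A reader might go further and infer that the SAE output mixes two observation windows, because AEs are defined "for participation in the study until the end of study visit" and protocol 7.2.1 begins "An SAE is defined as any adverse event". The documents do not support this. SAEs have a single stated collection window; the difference lies between non-serious AEs and SAEs, and SAP 2.5.1 does not call for a pooled table. The SAP states no onset window, but that is missing detail: protocol 7.1 has start dates recorded, protocol 9.5.2 summarizes by onset date, and table details are left to the shells.

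**Conclusion.** The point holds as a gap in completeness. SAEs in screen failures, and in enrolled subjects who did not inhale a capsule's contents, are collected but have no SAP output as written. The population for deaths is unclear.

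The conclusion rests on reading the 2.2 note as applying to listings and on the shells, which are not available here, not providing otherwise. The choking example further assumes that a subject who chokes on the first capsule would not be counted as having inhaled its contents.

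Two stronger inferences should not be drawn. One is that the SAE tables would be dominated by background hospitalisations after the visit. That would need an SAE rate the documents do not give, and they schedule no later contact at which such events would be sought. The other is that SAE tables must be limited to events starting during the visit. Nothing in the protocol requires that; showing onset relative to the visit lets the reader separate the two.

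The change is worth making because it is cheap and uses data already collected. It does not bear on the primary objective.

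**What to change.** - **SAP 2.2:** exempt the SAE and death listings from the Safety Set note. Keep the Safety Set for all summary tables.
- **SAP 2.5.1 and 2.5.2:** list all SAEs and deaths in consented subjects. Flag each subject as Safety Set, enrolled but not in the Safety Set, or screen failure, and give onset date relative to the visit.
- **Before database lock:** reconcile SAEs in the clinical database with the SAE Report Forms, and say in the SAP that the listings follow that reconciliation.

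The cost is a few lines of SAP text, one slightly longer listing and a reconciliation step. No new data, visits or subject contacts are needed.

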9.2 Patient demographics and other baseline characteristics

Appropriate descriptive statistics for demographics (age, sex, race and ethnicity), disease history, CF signs and symptoms - and previous medications will be presented to describe the study population overall and by the three age categories.

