9.5.2 Safety variables

Adverse events and SAEs will be coded according to the MedDRA coding system and summarized by system organ class (SOC) and preferred term by onset date within the study population overall and within each age group. For this purpose, the same event, as defined by preferred term, will be counted only once for each subject. AEs will also be summarized by

SOC, preferred term, and maximum severity within the study population overall and within each age group. AEs resulting in withdrawal of treatment will be summarized by SOC, preferred term.

Appropriate summary statistics will be provided for vital signs.

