2.5.4 Other safety data

2.5.4.1 Vital signs

Vital signs, including systolic and diastolic blood pressure, radial pulse rate, respiratory rate, and body temperature will be measured only once in the trial and will be summarized along with other baseline parameters ([Section 2.3](#)).

3 Sample size calculation

The FDA guidance document ‘Applying Human Factors and Usability Engineering to Medical Devices’ ([FDA 2016](#)) suggests a minimum of 15 subjects per distinct user group is required for validation testing. Per the guidance, “The FDA views populations as distinct when their abilities or the nature of their device interactions are expected to be different”. In the case of CF, age is the only characteristic which is likely to contribute to variation in abilities and/or device interaction. Therefore, the study will include 45 subjects with approximately 15 subjects in each of the three age groups (6-10 years, 11-17 years, and ≥ 18 years).

4 Change to protocol specified analyses

None

5 References

US Department of Health and Human Services, Public Health Service, Food and Drug Administration (2016) Applying Human Factors and Usability Engineering to Medical Devices

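### SAP 2.5.1 makes the AE and SAE summary tables conditional on five affected patients; the protocol sets no such condition, and SAP Section 4 declares no change

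*SAP*

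**What the plan says.** Protocol 9.5.2 has AEs and SAEs "summarized by system organ class (SOC) and preferred term by onset date within the study population overall and within each age group". It adds a summary by maximum severity, also overall and by age group, and a summary of AEs leading to withdrawal of treatment. Protocol Section 9 says in general terms that safety data, AEs and SAEs included, will be summarized descriptively. Neither place sets a minimum number of affected patients.

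SAP 2.5.1 begins in agreement: "AEs and SAEs will be summarized by system organ class (SOC) and preferred term (PT) for the safety set overall and by age subgroups". It continues: "The maximum AE severity and AEs resulting in withdrawal of treatment will also be summarized by SOC and preferred term". A Note then follows: "Summary tables will only be provided if at least five patients report any AE". No reason is given. The next sentence is not tied to the Note: "In addition to the tabulations, listings will be provided for AEs and SAEs".

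SAP Section 4, headed "Change to protocol specified analyses", states that there are none.

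A second item bears on Section 4. Protocol 9.2 closes its list of baseline summaries with "and previous medications will be presented to describe the study population overall and by the three age categories". SAP 2.4.2 codes prior as well as concomitant medications, but the tables it promises are these: "Standard summary tables of concomitant medications by ATC class and non-drug therapies will be provided".

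**The concern.** The protocol commits to a set of AE tables, and the SAP lets the observed AE count decide whether they exist. The Note stands after all the tabulations in SAP 2.5.1 and is not limited to any of them, so it covers the SAE, severity and withdrawal tables as well as the main AE table. It counts patients overall, not by age group and not by seriousness.

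The withdrawal table has some relevance in this study, because Protocol 5.6.2 names the emergence of AEs among the reasons for stopping study treatment.

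Because Section 4 reports no change, a reader of the study report who checked the SAP for departures from the protocol would be told there were none. At stake are the completeness of the planned safety tabulation and the accuracy of that declaration. The study's main conclusion is not at stake.

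**Working it through.** **Planned size.** Three age groups of about 15 give 3 × 15 = 45 completers, as stated in Protocol 9.8 and SAP Section 3. The plan enrolls 50, and 45/50 = 0.90, so a 10% allowance is implied. The safety set needs at least one inhaled capsule (SAP 2.2). I take its size as between 45 and 50.

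**Threshold as a proportion.** Five patients are 5/45 = 11.1% or 5/50 = 10.0%. Up to four affected patients can go untabulated: 4/45 = 8.9% (exact 95% CI 2.5% to 21.2%) or 4/50 = 8.0% (2.2% to 19.2%).

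**Probability that the tables are withheld.** Let X be the number of patients with any AE and p the true share of patients with one. Treating patients as independent,

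P(withheld) = P(X ≤ 4) = Σ (k = 0 to 4) C(n, k) p^k (1 − p)^(n − k).

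Neither document gives p. Protocol 3.7 says only that cough and bronchospasm may occur. The range below is an assumption.

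| Assumed p | n = 45 | n = 50 |
|---|---|---|
| 2% | 0.998 | 0.997 |
| 5% | 0.927 | 0.896 |
| 8% | 0.710 | 0.629 |
| 10% | 0.527 | 0.431 |
| 12% | 0.359 | 0.268 |
| 15% | 0.175 | 0.112 |
| 20% | 0.038 | 0.019 |
| 30% | 0.001 | <0.001 |

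Solving P(X ≤ 4) = 0.5 gives p = 10.3% for n = 45 and 9.3% for n = 50.

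**Is this only the case of no AEs at all?** No. The probability of one to four affected patients, so that there is something to tabulate but no table, is 0.828 (n = 45) or 0.819 (n = 50) at p = 5%, and 0.518 or 0.426 at p = 10%.

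**Clustering in one age group.** The threshold is overall, so four affected patients could all fall in one group of 15. That is 4/15 = 26.7% (exact 95% CI 7.8% to 55.1%), and no table by age group would follow. The same holds if all four had SAEs.

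**What stays unconditional.** AE and SAE listings (SAP 2.5.1), the death listing (SAP 2.5.2), vital signs (SAP 2.3 and 2.5.4.1), concomitant medication tables (SAP 2.4.2), and disposition with reasons for discontinuation (SAP 2.3). SAP 2.2.1 applies the age split to listings as well as tables.

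**The case against.** The strongest reply is that little is lost. When the Note applies, at most four patients have an AE, and each of their events is listed. The listings are presented by age subgroup, and SAP 2.3 reports the size of the safety set and its demographics by age subgroup. A reader could count the affected patients and form the proportions by hand. The threshold is fixed in advance, nothing is tested or compared, and SAP Section 2 treats the eCRF data as supplementary. The study's main result is the human factors assessment, which lies outside the SAP. All of this stands, and it keeps the severity low. It does not remove the conflict: the protocol promised the tabulation, the SAP makes it conditional, and Section 4 says nothing has changed.

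Four stronger readings are tempting, and the documents do not support them:

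- A reader might infer that the safety analysis will probably not be produced. Only the AE and SAE summary tables are conditional, and the probability falls below one half once about 9% to 10% of patients have an AE.
- A reader might infer that AE incidence is the only quantitative safety result. Protocol Section 9 counts vital signs and concomitant medications as safety data, and both are still summarized.
- A reader might suspect selective reporting. With every event listed whatever the count, none can be concealed.
- A reader might infer that the previous-medication and onset-date summaries have been dropped. SAP Section 2 leaves detail to a mock-shells document that is not available here, so the first cannot be settled. The second adds almost nothing in a one-day study.

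**Conclusion.** The conflict is real and rests on no assumption: a five-patient condition in SAP 2.5.1, none in Protocol 9.5.2 or Section 9, and no change declared in SAP Section 4. Only its practical effect depends on an assumption, namely the per-patient AE rate, with a safety set of 45 to 50 and independent patients. Within that, the chance of no tables runs from about nine in ten at a 5% rate to a few in a hundred at 20%. The loss is the protocol-specified tabulation of counts and percentages by system organ class, preferred term, severity and age group; the events themselves are still reported. Low severity, but worth correcting before the analysis.

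**What to change.** Delete the five-patient Note from SAP 2.5.1, so that the AE and SAE tables in Protocol 9.5.2 are always produced, overall and by age group. Declaring the Note in Section 4 with a reason would mend the record, but it would leave the protocol's tables conditional, so deletion is the cleaner course.

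Correct SAP Section 4 to list any protocol analysis that is really dropped. Check the mock shells for the previous-medication summary in Protocol 9.2; if it is not there, add it or list it.

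The cost is one deleted sentence, at most a line or two in Section 4, and a few short tables. No new data are needed and study conduct does not change.
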